Ongoing Psychiatric and Medical Assessments: The research psychiatrist will conduct weekly assessments of the psychiatric and medical status of the study participants. Participants who meet criteria for clinical worsening or the development of unacceptable medical or psychiatric risks will be removed from the trial and referred for appropriate treatment.

Study Assessments

Adverse Effects measures: The Systematic Assessment for the Treatment and Emergent Events (SAFTEE) (Johnson et al. 2005) adapted for buprenorphine and XR-NTX injections will be performed weekly to identify adverse symptoms.

Clinical Status measures: The Clinical Global Impression Scale-Observer (CGI) (Guy 1976) will be used to measure the overall clinical status of the participant as well change from baseline in the symptom severity. The Clinical Global Impression-Self (CGI-S) is a two-item scale that asks the subject to rate his or her current level of symptoms and estimate changes from baseline (Guy 1976).

Medical Evaluation and Monitoring: A medical history and physical exam will be performed during screening. Serum pregnancy testing will be performed during screening and urine pregnancy testing will be performed monthly during the study. Complete blood count, electrolyte, urinalysis, and liver function tests

will be performed during screening and monthly during the study. Height and weight will be measured and baseline body mass index (BMI) calculated during screening. Temperature, pulse, blood pressure, and weight will be measured at every study visit.

Mood and Anxiety measures: A structured interview version of the Hamilton Depression Scale (HAM-D) (Williams 1988) will be used to assess mood and anxiety symptoms at baseline and changes associated with treatment.

Psychiatric Evaluation and Diagnosis: The MINI International Neuropsychiatric Interview will be performed during screening and as part of a complete psychiatric diagnostic assessment.

Opiate Craving Scales- Self: A visual analog scales is used for patients to rate the intensity of craving experienced over the previous week for opiates (Bisaga, Sullivan et al. 2011).

Spielberger State-Trait Anxiety Test (SSTAT)- Self: The SSTAT is a well-validated measure of anxiety consisting of two self-rated subscales, one rating Trait anxiety and the other State anxiety (Spielberger, Gorsuch et al. 1970).

Beck Depression Inventory (BDI): The BDI is a 21-item self-report questionnaire. It has been used in many studies and validly and reliably assesses depression in many patient groups including substance abusers (Beck, Steer et al. 1996).

Subjective Opiate Withdrawal Scale (SOWS)- Self: The SOWS is a 19-item self-report scale reliably eliciting severity of common physical and mental symptoms of opiate withdrawal, and also yielding a total withdrawal severity score (Handelsman, Cochrane et al. 1987). It will be used to examine occurrence of symptoms resembling opiate withdrawal during naltrexone maintenance.

Risk Assessment Battery (RAB) The RAB provides a self-report measure of drug use, injection-related risk behavior, and sexual risk during the preceding six months (Navaline, Snider et al. 1994).

Please attach copies, unless standard instruments are used

Off label and investigational use of drugs/devices

Choose from the following that will be applicable to your study

Research Related Delay to Treatment

Will research procedures result in a delay to treatment?

No

Treatment to be provided at the end of the study

At the conclusion of the protocol, the participants will be offered supportive therapy for at

least one additional month or until an appropriate referral for on-going treatment is made. If the patient is interested to continue on XR-NTX, we will try to work with the patient's insurance to provide coverage to continue XR-NTX. If the patient wishes to be on oral naltrexone, we will provide him/her with a 30-day supply of oral medication, and will help patients to obtain referrals to treatment providers in the community.

Participants who had no response to naltrexone treatment, such as those who continued using opioids while on naltrexone as well as those who stopped taking naltrexone (missed scheduled injections) and/or resumed opioids after missing naltrexone, are considered to be at very high risk of a full relapse and overdose. These individuals will be immediately directed toward either inpatient detoxification followed by a residential treatment, or toward agonist maintenance with either buprenorphine/naloxone or methadone. Methadone maintenance treatment is widely available in the community; however, access to buprenorphine treatment is more restricted.

In order to minimize the risk of relapse due to the lack of access to the medication and the gap between treatment providers we would like to offer 2-week supply buprenorphine/naloxone 8mg to participants who are in the process of being referred out to either inpatient treatment or an agonist maintenance program. We will continue to provide additional support including frequent, daily if needed visits at our clinic for a maximum of 2 weeks.

Clinical Treatment Alternatives

Clinical treatment alternatives

Naltrexone maintenance and Relapse Prevention Therapy are effective and accepted treatments for opioid dependence. The major alternatives for outpatients with opioid dependence would be either methadone or buprenorphine/naloxone maintenance, which has a high success rate for patients willing to take it; injection naltrexone maintenance without research procedures; outpatient methadone detoxification; or inpatient detoxification followed by "drug-free" outpatient or residential counseling. Both inpatient and detoxification methods are associated with high relapse rates in the absence of antagonist maintenance.

Risks/Discomforts/Inconveniences

Risks that could be encountered during the study period

Risks of the Buprenorphine-Clonidine-Naltrexone Procedure: In this procedure, opiate-dependent patients are stabilized for 30 days on the partial opiate agonist buprenorphine. During subsequent administration of naltrexone and throughout the detoxification, withdrawal symptoms are treated with clonidine, an alpha-2-adrenergic receptor agonist which reduces sympathetic nervous system output produced by opiate withdrawal, clonazepam, a benzodiazepine which reduces the anxiety and dysphoria and permits sleep, and other prn medications such as trazodone or zolpidem for insomnia. Opiate withdrawal causes agitation, elevated pulse and blood pressure and other signs of sympathetic arousal, and sometimes confusion. Clonidine may produce somnolence or

hypotension. Clonazepam commonly may produce somnolence. **An extremely rare potential side effect of trazodone is priapism**. The procedure is conducted in a setting equivalent to a day hospital, with a STARS study physician present at all times, to permit close monitoring of vital signs and mental status.

Buprenorphine taper: The risks associated with buprenorphine dose reduction are minimal. During the buprenorphine taper, opioid withdrawal symptoms (e.g., anxiety, muscle aches, rhinorrhea) may emerge. If the participant does not tolerate well this discomfort, he or she will meet with the study physician, and discuss options (i.e. receiving more adjuvant medications, modifying a given daily dose of buprenorphine). The participant will also be offered the option of discontinuing the taper and transitioning to buprenorphine maintenance at a dose of buprenorphine/naloxone that is comfortable, which would mean discontinuation from the study and would be considered a treatment failure in terms of achieving opioid-free status. Medications will be dispensed by medical staff trained in the use of opioids, and in the management of adverse effects of opioids. The doses proposed for use in the current application are within the recommended dose range for treating opioid addiction.

Buprenorphine diversion and abuse: The use of buprenorphine in opioid-abusing, opioid-dependent volunteers is also associated with the risk of using the medication for the purposes of getting high. If sublingual buprenorphine is crushed and used parenterally, there is a risk of precipitated opioid withdrawal, due to the release of the sequestered naloxone. Attempts to administer buprenorphine by injection have also been associated with granulomatous reactions and infections. Participants will be warned of the risks of diversion and abuse and advised not to use the medication in this manner. They will also be warned of the risks of accidental ingestion. If it is determined that patients have been abusing their buprenorphine in such a manner, they will be removed from the study and referred to methadone maintenance.

Side Effects of Naltrexone: The possible side effects of naltrexone may include difficulty sleeping, anxiety, nervousness, abdominal pain/cramps, nausea and/or vomiting, low energy, joint muscle pain, and headaches. It is important to note that these symptoms may represent protracted opioid withdrawal symptoms. The most common adverse events associated with XR-NTX in clinical trials for alcohol dependence were nausea, vomiting, headache, dizziness, asthenic conditions and injection site reactions. Cases of urticaria, angioedema, and anaphylaxis have been observed with use of XR-NTX.

Naltrexone has been associated with reversible hepatocellular injury indicated by elevated liver enzymes when administered at doses substantially greater than the 50 mg per day dose recommended for maintenance treatment of opiate dependence and proposed for the present studies. When used in the recommended dose range in opiate-dependent patients, this risk is remote (Brahm et al 1988). Naltrexone is therefore contraindicated in patients with acute hepatitis or liver failure, and such patients are excluded from the study. Patients with hepatic enzyme levels greater than two times the upper limit of normal are therefore excluded. Liver enzymes will be repeated frequently. Depot naltrexone achieves higher bloodlevels than oral naltrexone initially, but these should remain lower than levels associated with hepatitis. If naltrexone-induced hepatitis were to occur in the setting of a long-acting preparation, where the naltrexone would be only very slowly eliminated, this would prolong exposure to the offending agent. However, our experience with long-acting naltrexone also suggests it is safe. In our studies with long-acting naltrexone several patients experienced elevation in liver enzymes, which were determined to be related to hepatitis C. One patient developed diabetes mellitus,

which was deemed unlikely to be study related. In the proposed study we will use a long-acting, injectable preparation of naltrexone (Vivitrol 380 mg). This preparation has been used in a large clinical trials as a treatment for alcohol dependence and is considered to have a good safety profile (Garbutt et al 2005). XR-NTX is currently approved by the FDA for the treatment of alcohol dependence.

If a patient misses a scheduled injection of XR-NTX and resumes regular opiate use, then taking a dose of naltrexone will precipitate opiate withdrawal, which may be quite severe in proportion to the time since the last naltrexone dose and the level of opiate dependence. Patients will be warned not to take the naltrexone if they have missed their dose for more than a week and resumed opiate use for more than two days. They will be

instructed instead to contact their therapist and/or research psychiatrist, who will see the patient and perform a naloxone challenge test to determine whether or not naltrexone can be safely resumed.

Patients who fail two consecutive naloxone challenges (withdrawal is precipitated), are considered to have relapsed and are referred for inpatient detoxification.

Self-administration of large doses of opiates may over-ride the blockade produced by naltrexone resulting in an opiate overdose with its attendant risks, including respiratory depression and death. Patients will be warned of the severe danger of using opiates, including trying to over-ride the blockade. Also patients who have stopped naltrexone and resume opiates will not be tolerant initially, so that the quantities of opiates self-administered prior to treatment, when they were tolerant, may be quite dangerous in the non-tolerant state. Patients will be warned of this. Patients who self-administer opiates to the point of somnolence or stupor will be removed from the trial and referred to inpatient detoxification or agonist maintenance treatment. Until such patients are accepted for treatment elsewhere, they will remain in treatment at our clinic, where they will be offered therapy and treated in the open label manner for the duration of trial.

In the event of a medical emergency requiring opiate analgesia, a patient on naltrexone will require higher doses of opiates than normally administered. Patients will be informed of this and will be given a naltrexone medication card to carry in their wallet.

Naloxone Challenge Test: This test will be performed under the supervision of a study physician and will take approximately 45 min to complete. The risks of a dose of 0.2-0.8 mg naloxone administered IM are the signs and symptoms associated with opioid withdrawal ("gooseflesh," "vomiting," "tremor," "uncontrollable yawning," etc.). These will be assessed every 10 min. for up to 45 min. During the procedure, we will measure blood pressure and heart rate before and up to 30 min. after the naloxone dose.

Pregnancy: Both the buprenorphine-clonidine-naltrexone procedure and naltrexone maintenance are considered contraindicated in pregnancy. Several small case series (Hulse et al., 2001; 2004) are reassuring in suggesting favorable pregnancy outcomes in women detoxified and maintained on naltrexone while pregnant. However, standard practice suggests methadone maintenance is the treatment of choice for opioid dependent pregnant women, and we do not consider the small size of these case series sufficient to amend that recommendation. Absence of pregnancy will be confirmed at baseline and monthly during the study with urinary HCG. During the inpatient detoxification period, a serum (quantitative) pregnancy test will be obtained on admission and repeated on the day prior to administration of depot naltrexone. For women, regular use of an adequate contraception method (diaphragm with spermicide, condom with spermicide, birth control pills) is required for inclusion in the study. Patients who become pregnant during the trial

will be removed from the trial and treated as clinically indicated.

Blood Tests: Blood drawing may cause slight discomfort at site of needle entry, resulting in a small bruise. Other risks include patients' discomfort with being asked uncomfortable questions or the psychological distress that may occur if a patient agrees to be tested for HIV.

Risks associated with receiving vouchers or cash equivalents: An incentive system is being used to compensate patients for their time and travel and to encourage compliance with study procedures. For that purpose we have adopted procedures used widely in the context of Contingency Management Therapy. We believe that using low-value incentives is essential to maximize participation in study-related procedures, including nursing and physician visits for safety monitoring, study outcomes collection, and therapy participation. Risks that participants will attempt to use study payments to purchase drugs, though still present, are rather small with current procedures.

Describe procedures for minimizing risks

The exclusion criteria of this study are designed to minimize the risks to participants.

Patients are excluded if they have severe psychiatric illness (mood disorder with functional impairment or suicide risk, schizophrenia) which might interfere with their ability to participate in the outpatient therapy. A history of drug overdoses will be exclusionary. Pregnancy, lactation, or failure to practice a reliable birth control method is exclusionary, and patients are instructed to inform their psychiatrist immediately if they suspect they may be pregnant. Urine HCG is tested during screening and monthly throughout the trial. Serum (quantitative) pregnancy test will be obtained during screening. The baseline medical evaluation includes physical examination, blood chemistry profile (including liver function tests), complete blood count, urinalysis (including HCG), and electrocardiogram, urine toxicology, and naloxone challenge if opiate dependence diagnosis is unclear. The evaluating psychiatrist reviews all these and takes a medical history. Any disorders which might make buprenorphine-clonidine-naltrexone or naltrexone maintenance hazardous, such as uncontrolled hypertension, diabetes, heart disease, hepatitis with transaminase levels greater than three times the upper limit of normal, renal disease, or advanced AIDS are exclusionary. Patients with acute hepatitis infection and increasing liver function tests during screening will be excluded from study participation. The patient will be assisted in obtaining appropriate medical evaluation and treatment, and may be eligible for the research study once the problem is controlled. History of an allergic reaction to any of the medications used is an exclusion criterion.

Patient Education: All patients will be informed through the informed consent form and discussions with the research psychiatrist of the possible side effects and risks enumerated above. In addition, at weekly visits the psychiatrist will query side effects in general, and events of specific concern including missing naltrexone doses in conjunction with resumed opiate use or heavy opiate use in an effort to over-ride the blockade, and the risk of overdose and death in these situations. Patients will give informed consent before entering the study. Patients are instructed to call us if any untoward effects occur and are given the phone number of our 24-hour answering service.

Patient Monitoring and Removal from Study: The psychiatrist and/or therapist will assess appropriateness for continuation in the research study on a continuous basis, and will remove

from the trial patients with significant clinical deterioration or noncompliance of a type which could be dangerous.

Methods to Protect Confidentiality

Describe methods to protect confidentiality

A Certificate of Confidentiality has been acquired for this study from the National Institute on Drug Abuse to offer protection for the privacy of subjects by protecting identifiable research information from forced disclosure (e.g., through a subpoena or court order). The Certificate of Confidentiality allows investigators and others with access to research records to refuse to disclose information that could identify subjects in any civil, criminal, administrative, legislative, or other proceeding, whether at the Federal, State, or local level. The Certificate of Confidentiality is granted for studies that collect information that, if disclosed, could damage subjects' financial, employability, insurability, or reputation, or have other adverse consequences.

We use coded records (i.e. initials and numbers), store signed consent forms in a locked safe, and try, to the best of our ability to maintain confidentiality. Only coded records will be entered into the computer and the security of electronic data is ensured at the level of the server, the user, and the database. We do, however, point out to prospective patients, that we cannot assure that their drug histories and other personal records might not become known.

Will the study be conducted under a certificate of confidentiality?

Yes, we have already received a Certificate of Confidentiality

Direct Benefits to Subjects

Direct Benefits to Subjects

Participants may benefit from many of the components of the treatment that they receive, including buprenorphine stabilization, induction onto injection naltrexone, naltrexone maintenance, and components of behavioral therapy.

Further, because participants are recruited from the pool of participants that fail XR-NTX induction as part of one of two trials, an additional potential benefit is a decrease in time to treatment following study discontinuation from the parent protocols (IRB #6734 or IRB #7190). Immediately following discontinuation from the initial protocol, participants are eligible for the current protocol and if enrolled can be stabilized on buprenorphine, thereby potentially reducing overdose risk, in a more timely fashion than if referred to treatment in the community.

Compensation and/or Reimbursement

Will compensation or reimbursement for expenses be offered to subjects?

Yes

Please describe and indicate total amount and schedule of payment(s).

Include justification for compensation amounts and indicate if there are bonus payments.

Participants will receive \$10 for completion of study assessments at each visit and will receive compensation for travel (\$5 per visit). They will also be offered \$25 for completing a follow-up visit at week 12 and will receive \$5 for travel. Thus participants could earn up to \$480 for completion of study assessments and reimbursement for travel.

References

References

- Caldiero RM, Parran TV Jr., Adelman CL, Piche B. (2006). Inpatient initiation of buprenorphine maintenance vs. detoxification: can retention of opioid-dependent patients in outpatient counseling be improved? *Am J Addict* 15(1):1-7.

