3 R01 DA030484-04S1

Select one of the following

Single Site

Business Office

RFMH

Does the grant/contract involve a subcontract?

No

Study Location

Indicate if the research is/will be conducted at any of the following

- Other Columbia University Medical Center Facilities

This protocol describes research conducted by the PI at other facilities/locations

No

Lay Summary of Proposed Research

Lay Summary of Proposed Research

We will randomize **46** opioid-dependent participants who have initially failed outpatient induction onto XR-NTX; participants will receive buprenorphine/naloxone on a weekly basis for 30 days.

Buprenorphine/naloxone will be dispensed weekly during the 30-day stabilization and twice weekly during taper phase, and all patients who successfully complete the detoxification will be offered induction onto XR-NTX. All participants will receive weekly therapy with a study psychiatrist. All participants will receive open-label medication. The primary outcome of this study will be percentage of patients successfully inducted onto XR-NTX. Secondary outcomes will be time to relapse, defined as opioid use or dropout.

Background, Significance and Rationale

Background, Significance and Rationale

Rates of prescription opioids and heroin use and related morbidity and mortality continue to grow at an alarming rate (CDC, 2012; SAMHSA, 2013), and there are currently more than 2.5 million individuals affected in the U.S. While heroin use remains prevalent, prescription opioid abuse has risen dramatically in the past decade (SAMHSA, 2012). There has also been a dramatic increase in unintentional overdose deaths (CDC, 2012). Unfortunately, most people with opioid dependence are not receiving treatment (SAMHSA, 2013). Reasons for this gap between treatment need and delivery include lack of access to opioid dependence treatment programs, lack of training for providers such that the healthcare workforce is not, for the most part, knowledgeable about effective treatment options. Expanding available treatment options and attracting more opioid-dependent individuals into effective treatment represent important public health priorities (CASA Columbia, 2012).

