In another one of our ongoing studies, A Phase 3 Study to Evaluate the Safety, Tolerability, and Efficacy of Naltrexone for use in Conjunction with Buprenorphine in Adults with Opioid Use Disorder Prior to First Dose of Vivitrol (PI: [name], (#7190) opioid-dependent participants are randomized to one of three outpatient 8-day detoxification schedules: (1) oral naltrexone + buprenorphine (2) oral naltrexone+ placebo buprenorphine (3) placebo oral naltrexone + placebo buprenorphine. All three groups receive a single administration of a long-acting injectable naltrexone (XR-NTX) on Day 8.

Therefore, in the current pilot study, we would like to implement a procedure for retaining in treatment patients who fail the initial attempt at outpatient detoxification and XR-NTX induction. This procedure will

be similar to the approach of Sigmon et al. 2013, with a 4-week period of buprenorphine stabilization and taper off. Participants will then repeat the detox using a 2-day washout followed by a 4-day ascending taper of oral naltrexone (1, 3, 12, and 25 mg), with the purpose of XR-NTX induction. Including a buprenorphine maintenance arm allows for a period of stabilization and relief from withdrawal symptoms, followed by a taper, with the thought that this may be more tolerable to these individuals that have previously had a difficult time modulating and tolerating the distress of the more rapid detoxification.

Specific Aims and Hypotheses

Specific Aims and Hypotheses

SPECIFIC AIM #1: To test the efficacy of a second-line treatment for the 50% of opioid-dependent individuals who fail their first attempt at outpatient XR-NTX induction. The primary outcome is successful induction onto XR-NTX.

EXPLORATORY AIMS: We will also examine secondary outcomes retention (time to drop-out); severity of opioid withdrawal; and 2-week abstinence at 3rd and 4th weeks after XR-NTX injection.

Description of Subject Population

Sample #1

Specify subject population

Adults 18-60 years old, who meet current DSM-5 criteria for OUD of at least moderate severity

Number of completers required to accomplish study aims

14

Projected number of subjects who will be enrolled to obtain required number of completers

46

Age range of subject population

18-60

Gender, Racial and Ethnic Breakdown

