Naltrexone induction procedure: Participants who successfully complete the taper must then complete a two-day washout (abstinence for opioids, buprenorphine). During this 48-hr period, participants will report to the STARS clinic daily for vital sign monitoring and to receive ancillary medications (clonidine, clonazepam, zolpidem, prochlorperazine) to alleviate withdrawal and discomfort as needed. After abstinence of $>/=48$ hours from the last buprenorphine dose, to allow for mu receptor availability, participants will begin the naltrexone induction, using a 4-day ascending taper of oral naltrexone (1, 3, 12, and 25 mg), followed by injection naltrexone. The administration of naltrexone will occur within a detoxification suite provided at STARS, consisting of a private room outfitted with two comfortable reclining lounge chairs for resting, adjustable lighting, and an entertainment system. Participants will be monitored by clinical staff at least every 1-2 hours with frequent vital signs checks and withdrawal assessments. A research psychiatrist or study physician will be present at all times to conduct frequent clinical assessments and provide adjuvant medications and naltrexone. Patients will be monitored on a daily basis (Monday to Friday) for up to 8 hours per day. Transportation home by car service will be provided at the end of the day for any patient deemed to have this clinical need.

As per the dosing schedule in the protocol #6374, on Day 1 of the naltrexone induction, participants are pre-treated with prochlorperazine 10 mg for nausea, followed by the first dose of naltrexone 1mg. Ascending doses of naltrexone will then be titrated upward slowly (3mg, 12mg, 25mg). Adjuvant medications will be available to patients and will include clonidine for myalgias, prochlorperazine for nausea, clonazepam to reduce anxiety and dysphoria, and trazodone or zolpidem for insomnia. Participants will be provided take-home doses of adjuvant medications in small doses and on a tapering schedule for one week post-administration of XR-NTX. Participants will be required to visit the clinic daily and remain there for at least 1 hour to permit close monitoring, with an option to stay as long as necessary to achieve relief of symptoms and medical stability prior to being discharged home.

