**Statistical Analysis:**

This is a single-arm, open-label, pilot study evaluating whether individuals with opioid use disorder who were unable to tolerate a rapid transition to XR-naltrexone would tolerate a slow four-week buprenorphine taper and XR- naltrexone induction.

Study objective was to evaluate the feasibility of the slow-transition protocol and to obtain descriptive data regarding baseline demographics and treatment outcomes in such patients.

Analytical plan include: 1) percent of participant who completed the transition, 2) time to relapse defined as daily opioid use for 5 days or study dropout, and 3) descriptive statistics on baseline characteristics comparing participants who successfully initiated XR-NTX and those who did not initiate XR-NTX. Summary statistics will include frequency, percentages, and where relevant averages.

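### Aim 1 and the lay summary describe an efficacy test and randomization that this single-arm feasibility pilot does not have, and the primary percentage is planned without an interval

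*Protocol*

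**What the plan says.** **Protocol, Specific Aims and Hypotheses.** Aim 1 is "To test the efficacy of a second-line treatment for the 50% of opioid-dependent individuals who fail their first attempt at outpatient XR-NTX induction", with successful induction onto XR-NTX as the primary outcome.

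**Protocol, Lay Summary.** The opening sentence reads "We will randomize 46 opioid-dependent participants who have initially failed outpatient induction onto XR-NTX". The same section then describes one regimen and adds "All participants will receive open-label medication" and "all patients who successfully complete the detoxification will be offered induction onto XR-NTX".

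**Protocol, Background.** The last paragraph is more modest: "in the current pilot study, we would like to implement a procedure for retaining in treatment patients".

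**SAP, Statistical Analysis.** It opens "This is a single-arm, open-label, pilot study". It gives feasibility and descriptive data as the objective, and its first planned analysis is "percent of participant who completed the transition". Results are to be summarised by frequencies, percentages and, where relevant, averages. No test, reference rate or confidence interval is mentioned.

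**The concern.** An aim of testing efficacy implies a contrast, either with a concurrent group or with a stated rate that the treatment must beat. Randomization implies at least two arms. A reader who has only the aim and the lay summary would expect a controlled comparison and could take the induction percentage as its result. An uncontrolled series with no benchmark cannot support that claim.

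The second issue is precision. If the objective is to describe how often the procedure works in these patients, the estimate is the study's main product. A percentage from about 30 people printed without an interval looks firmer than it is. Both matters are still live, because the continuation form says the data are being analysed and a manuscript is in preparation.

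**Working it through.** **1. Is there a second arm?** Study Procedures gives one buprenorphine/naloxone stabilization and taper schedule, one washout, one oral naltrexone sequence and one injection plan, for everyone. There is no allocation ratio, randomization method or control regimen for this study. Apart from the Lay Summary verb, randomization language in the protocol refers to the parent protocols (#6374, #7190) or to cited literature. Background does speak of a buprenorphine maintenance arm, but the sentence describes the stabilization and taper that all participants receive. The SAP's single-arm description fits the procedures; the Lay Summary verb does not.

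**2. Is there a reference rate?** The only induction rates given are those of parent study #6374: about 50% overall, and 53% against 42% by arm. They are first-attempt rates, whereas inclusion criterion 6 here requires that the first attempt failed. The documents do not adopt them as a benchmark, and the two populations differ by construction.

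**3. Is there a sample-size argument?** Description of Subject Population gives 14 completers from 46 enrolled, which is 14/46 = 30.4% completion. No alpha, power, null rate or target precision accompanies these figures, so there is no test calculation to reproduce.

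**4. How precise will the percentage be?** Overall Progress reports 30 enrolled and 8 who completed the study. Interventions are finished and nobody consented in the past year, so n = 30 is taken as final. The exact (Clopper-Pearson) 95% limits for x successes in n are:

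- lower = 2.5% quantile of Beta(x, n − x + 1)
- upper = 97.5% quantile of Beta(x + 1, n − x)

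| x/n | Percentage | Exact 95% CI | Width (points) |
|---|---|---|---|
| 8/30 (assumes the 8 study completers are those inducted) | 26.7% | 12.3% to 45.9% | 33.6 |
| 15/30 (illustrative; widest case at n = 30) | 50.0% | 31.3% to 68.7% | 37.4 |

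The number inducted is not stated. Because follow-up runs through Week 12 after induction, the 8 completers may be fewer than those inducted. The 37-point maximum needs no such assumption.

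**5. What would an efficacy verdict rest on?** Take the same assumed 8/30 and calculate the one-sided exact binomial probability of 8 or more successes under assumed reference rates: 0.008 at 10%, 0.07 at 15%, 0.24 at 20% and 0.72 at 30%. None of these rates is in the documents. The same data would look convincing or empty depending on a number that nobody has set.

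**The case against.** The strongest reply is that the SAP governs the analysis and already states everything needed: single arm, open label, pilot, feasibility, descriptive statistics. The protocol calls itself a pilot shortly before Aim 1, and the sentence containing *randomize* describes only one regimen. On this view the wording misleads nobody who reads on, an interval is good practice rather than a requirement in a descriptive pilot, and readers can compute one themselves.

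Much of this stands. No invalid test is planned, a descriptive SAP suits a pilot, and leaving out an interval biases nothing. The SAP also already plans the frequency, so the count is not missing. What remains is that the primary aim and the lay summary state properties the study lacks, and that the planned summary of the primary outcome leaves out its uncertainty.

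A reader might go further and infer that the denominator is open: since "Participants who successfully complete the taper must then complete a two-day washout", the percentage could be taken among taper completers only. The documents do not support that. The SAP's first sentence makes the taper part of what is being evaluated, and its third item divides participants into those who did and did not initiate XR-NTX. The Risks section (Buprenorphine taper) classes a participant who stops the taper for buprenorphine maintenance as a treatment failure, not as someone outside the analysis. All participants is the plain reading, and the order of procedures does not define an analysis set.

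**Conclusion.** The point holds as a minor one, in two parts.

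- **Wording.** Aim 1 and one verb in the Lay Summary conflict with the procedures and with the SAP. This follows from the text alone and needs no assumption.
- **Precision.** The primary percentage is planned without an interval. At n = 30 the exact 95% interval can be up to 37 points wide. The 27% (12% to 46%) figure is illustrative and depends on treating study completers as those inducted.

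It would be too strong to say that the trial plans an unsupported efficacy analysis, that a randomization was omitted, or that the denominator is undefined. The SAP plans no test, the procedures contain no second arm, and the denominator is clear enough that one confirming phrase will do.

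**What to change.** Issue a short dated clarification, disclosed as made after data collection, with the existing text left visible:

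1. Restate Aim 1 as estimating the percentage of all enrolled participants who receive the first XR-NTX injection, and say that no efficacy claim against another strategy will be made.
2. In the Lay Summary, replace *randomize* with *enrol*.
3. In SAP item 1, add an exact (Clopper-Pearson) 95% confidence interval to the planned frequency and percentage, with all enrolled participants as the denominator. Count anyone who leaves before the injection as not inducted. This agrees with the protocol's treatment-failure rule for those who stop the taper for maintenance. For other early leavers it is a proposed convention and should be labelled so.

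Carry the same wording into the manuscript.

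The cost is a few sentences and one computed interval, with no new data and no change to procedures or to the planned analyses. The downside is a more modest and visibly imprecise claim, and a clarification that must be acknowledged as post hoc.
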